9.11 Safety Analyses

All subjects who have received at least one dose of study drug (the “safety population”) will be included in the safety analyses. Statistical summary analysis of safety data will be descriptive and performed by treatment group and by stratum (age and gender groups). No inferential hypothesis testing will be performed on the safety variables with the exception of serum calcium, serum phosphorus, serum CaxP product and urine calcium to creatinine ratio.

9.11.1 Primary Endpoints Analyses

9.11.1.1 Adverse Events

All AEs will be collected on the eCRF and coded via SOC and preferred term using MedDRA version 20.0 or higher. After randomization, AEs with missing onset date will be treated as TEAEs and missing onset date will be imputed as the date of study drug administration, unless the event end date indicates that the event resolved prior to administration of study drug, in which case it will be documented in medical history. AEs with partial onset date will be treated as TEAEs unless the partial onset date or end date of the event is complete enough to indicate that the event started or resolved prior to the administration of study drug, in which case it will be documented in medical history. Detailed information collected for each TEAE will include: AE number, a description of the event, start date, end date or ongoing as of date, outcome, therapy for event, whether the AE was serious, seriousness criteria (life-threatening, death, hospitalization/prolongation of hospitalization, congenital anomaly, persistent or significant disability/incapacity, required intervention to prevent permanent impairment/damage), severity, and relationship to study drug. The incidence of the AEs will be summarized by treatment group for all TEAEs, potentially drug-related TEAEs, serious TEAEs, discontinuation due to TEAEs, TEAEs by relationship to study drug (definite, probable, possible, unrelated) and TEAEs by severity (mild, moderate, severe). The number and percentages of subjects with a TEAE will be summarized by SOC and preferred term and presented overall and by treatment group. TEAEs will be sorted in descending order of total incidence of SOC and preferred term within each SOC. The percentages will be based on the number of ITT subjects in a particular treatment group. If a subject has more than one TEAE that code to the same preferred term, the subject will be counted only once for that preferred term. Similarly, if a subject has more than one TEAE within a SOC category, the subject will be counted only once in that SOC category. All AEs collected on the eCRF will be included in the listings. An additional listing of all subject deaths will also be provided.

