Safety and tolerability will be evaluated in the safety population by AEs, PEs, VS, hematology and clinical chemistries, and ECGs.

Pharmacokinetic Endpoints:

For the interim analysis, repeated-dose (steady-state) PK determinations will be performed in subsets of subjects in both Cohort 1 and Cohort 2 by analyzing serum 25-hydroxyvitamin D₃ concentrations versus time recorded during dosing with CTAP101 Capsules (n=10) or placebo (n=5) in the last three days of the 12th week of treatment.

For the final analysis, repeated-dose (steady-state) PK determinations will be performed in both Cohort 1 and Cohort 2 by analyzing serum 25-hydroxyvitamin D₃ concentrations versus time recorded (a) during dosing with CTAP101 Capsules or placebo in the last three days of the 12th week of treatment and (b) after the last administered dose in each active treatment group.

The following PK parameters will be calculated using observed and baseline-adjusted 25-hydroxyvitamin D₃ concentrations: (a) area under the concentration curve (AUC), maximum concentration, (C_{\max}), time to maximum concentration (t_{\max}), and steady-state concentration (C_{ss}); and (b) $t_{1/2}$, clearance (CL/F) and volume of distribution (Vd/F), as feasible. Relative exposure and dose proportionality will be examined, if possible.

Secondary Endpoints:

Secondary efficacy endpoints include the proportion of subjects in the per-protocol (PP) population attaining a mean decrease in plasma iPTH of at least 30% from pre-treatment baseline during the EAP and the proportions of subjects in the ITT and PP populations attaining a mean serum total 25-hydroxyvitamin D of at least 30 ng/mL, in aggregate and by mean weekly study dose in the EAP. Additional secondary endpoints include the time courses of mean absolute changes from pre-treatment baseline in serum total 25-hydroxyvitamin D and plasma iPTH; PD effects on mean serum calcium (corrected), serum phosphorus, serum CaxP product, and the urine calcium:creatinine ratio; the proportion of subjects in each treatment group with hypercalciuria (>200 mg calcium/g creatinine), hypercalcemia (2 consecutive visits with serum calcium >10.3 mg/dL) or hyperphosphatemia (2 consecutive visits with serum phosphorus >5.5 mg/dL (ages 12 to <18 years) or >6.0 mg/dL (ages 8 to <12 years), deemed to be study drug related); and the proportion of subjects who attain 2 consecutive plasma iPTH values ≤ 70 pg/mL.

[REDACTED]

[REDACTED]

[REDACTED]

Additional Assessments:

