Secondary efficacy will be assessed in the PP population by comparing the proportions of subjects in each active treatment group attaining mean decreases in plasma iPTH of $\geq 30\%$ (from baseline) in the EAP to the corresponding proportion of subjects in the placebo group, and in the ITT and PP populations by comparing the proportions of subjects in each active treatment group attaining mean serum total 25-hydroxyvitamin D of ≥ 30 ng/mL in the EAP to the corresponding proportions of subjects in the placebo group, in aggregate and by mean weekly study dose in the EAP. Mean weekly dose in the EAP will be calculated for three groups of subjects: those receiving 0 mcg per day; those receiving >0 and ≤ 30 mcg per day; and, those receiving >30 mcg/day of calcifediol.

Primary safety analyses will be conducted in the ITT population, and the statistical summary will be descriptive and performed by treatment group. No inferential hypothesis testing will be performed on the safety parameters with the exception of serum calcium, serum phosphorus, serum CaxP product, and urine calcium:creatinine ratio.

Secondary safety analyses will compare the proportions of subjects with confirmed corrected serum calcium >10.3 mg/dL or confirmed serum phosphorus >5.5 mg/dL (ages 12 to <18 years) or >6.0 mg/dL (ages 8 to <12 years) (deemed to be study drug related) or serum confirmed CaxP product >55 (for Cohort 1) or >60 (for Cohort 2) between the CTAP101 Capsules and placebo treatment groups using the Cochran-Mantel-Haenszel test statistic (alpha=0.05) for overall safety in the multicenter results.

Descriptive statistics will be applied to evaluate patient reported palatability and acceptability.

Inclusion Criteria:

Each subject must meet the following criteria to be enrolled in this study:

1. Cohort 1: Be 12 to <18 years of age and have a body weight of ≥ 40 kg; Cohort 2: be 8 to <12 years of age and have a body weight of ≥ 20 kg.
2. Be diagnosed with stage 3 or 4 CKD at least six months prior to the screening visit, and have an estimated glomerular filtration rate (eGFR) of ≥ 15 to <60 mL/min/1.73m² at screening.
3. Be without any disease state or physical condition that might impair evaluation of safety or which, in the investigator's opinion, would interfere with study participation, including:
 - a. Serum albumin ≤ 3.0 g/dL;

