6.6.9 Treatment-Emergent Adverse Events

A TEAE is defined as any adverse event with onset or worsening reported by a subject from the time that the first dose of study drug is taken until 30 days following discontinuation of study drug administration.

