9.3 Analysis Populations

9.3.1 Analysis Populations

Efficacy analyses will be conducted for the ITT and PP, as indicated. The ITT population will be defined as all subjects who have been randomized to receive study medication. The PP population will be defined as all subjects who have at least two plasma iPTH determinations included each in the calculated baseline value and in the EAP, defined as weeks 20 through 26 (visits 19-22). Safety analyses will be conducted in the safety population, defined as all randomized subjects who have received at least one dose of the study drug.

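### The plan names two populations for the same safety tables, and the ITT denominator for TEAE percentages would understate incidence if any randomized subject is never dosed

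*Combined protocol and SAP*

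**What the plan says.** Three places assign safety to treated subjects. Section 9.3.1 conducts safety analyses in "the safety population, defined as all randomized subjects who have received at least one dose of the study drug". Section 9.11 repeats this for the whole safety section: "All subjects who have received at least one dose of study drug" are the subjects to be included. The synopsis, under Primary Safety Endpoints, agrees: "Safety and tolerability will be evaluated in the safety population by AEs, PEs, VS, hematology and clinical chemistries, and ECGs".

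Two places say otherwise. Section 9.11.1.1, which sits under 9.11, says of the TEAE tables: "The percentages will be based on the number of ITT subjects in a particular treatment group". The synopsis, under Statistical Analyses, says: "Primary safety analyses will be conducted in the ITT population". Section 9.3.1 leaves no doubt that ITT is the wider set: "The ITT population will be defined as all subjects who have been randomized to receive study medication".

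Section 6.6.9 fixes when a TEAE can begin: "from the time that the first dose of study drug is taken", with the window closing 30 days after study drug is discontinued.

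**The concern.** A programmer cannot follow all five statements. The general denominator rule in Section 9.1 does not settle the matter: it defers to any more specific instruction, and Section 9.11.1.1 gives one, naming ITT.

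The choice also has a direction. A randomized subject who never takes study drug adds one to an ITT denominator. Because the TEAE window opens at first dose, that subject ordinarily adds nothing to the numerator. The reported percentage then falls below the rate among those exposed, and by a different proportion in each arm unless the undosed fractions happen to match. Safety and tolerability is a primary objective (Section 2.1.1), so the denominator should be settled before the data are unblinded.

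**Working it through.** The plan states no TEAE rate and no count of undosed subjects, so there is no figure to reproduce.

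**Inputs.** Planned arm sizes are N = 72 active and N = 36 placebo (Section 9.2). The ITT and safety definitions are in Section 9.3.1, and the TEAE window is in Section 6.6.9. The number never dosed, u, is not in the documents; I assume 0 to 4 per arm. The number of subjects with a TEAE, k, is also assumed, chosen as the whole number nearest 30% of treated subjects.

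**Formula.** ITT percentage = 100k/N. Safety-population percentage = 100k/(N-u). The ratio of the first to the second is (N-u)/N.

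| Arm | u | Factor (N-u)/N | ITT % | Safety % | Shift (points) |
|---|---|---|---|---|---|
| Active | 0 | 1 | 22/72 = 30.6 | 22/72 = 30.6 | 0 |
| Active | 1 | 71/72 = 0.986 | 21/72 = 29.2 | 21/71 = 29.6 | 0.4 |
| Active | 2 | 70/72 = 0.972 | 21/72 = 29.2 | 21/70 = 30.0 | 0.8 |
| Active | 4 | 68/72 = 0.944 | 20/72 = 27.8 | 20/68 = 29.4 | 1.6 |
| Placebo | 0 | 1 | 11/36 = 30.6 | 11/36 = 30.6 | 0 |
| Placebo | 1 | 35/36 = 0.972 | 10/36 = 27.8 | 10/35 = 28.6 | 0.8 |
| Placebo | 2 | 34/36 = 0.944 | 10/36 = 27.8 | 10/34 = 29.4 | 1.6 |
| Placebo | 4 | 32/36 = 0.889 | 10/36 = 27.8 | 10/32 = 31.3 | 3.5 |

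**Between arms.** Take a treated-subject rate of exactly 30% in both arms. With u = 2 in each, the ITT figures are 30 × 70/72 = 29.2% and 30 × 34/36 = 28.3%, an apparent gap of 0.8 points where there is none. If the undosed counts follow the 2:1 allocation, for instance u = 4 active and u = 2 placebo, both factors are 0.944 and equal rates stay equal.

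**Exception in the numerator.** Section 9.11.1.1 treats a post-randomization event with no onset date as a TEAE and imputes its onset to the date of study drug administration. An undosed subject has no such date, and the rule does not exclude that subject. If v undosed subjects were counted this way, the ITT percentage would be 100(k+v)/N. With N = 72, u = 2, k = 21 and v = 1, that is 22/72 = 30.6%, against 21/70 = 30.0% on treated subjects. So in a rare case the error could reverse.

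**The case against.** The strongest reply is that this may be only a drafting slip with no numerical effect. Three statements name the safety population against two for ITT, so the intended set is fairly clear. Randomization and dispensing both happen at Visit 3 (Section 7.1.3) and dosing is at bedtime (Section 5.3), so the gap in which a subject could drop out undosed is short. If everyone takes a dose, the two populations coincide. AE summaries are descriptive, with no hypothesis test planned on TEAE incidence (Section 9.11), and the primary efficacy analysis is untouched.

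Most of that stands, and it limits the point. It does not remove it: the only explicit instruction on the TEAE denominator names the wrong set, and the general rule in Section 9.1 yields to it.

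Several stronger readings are tempting, and the documents do not support them:

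- A reader might infer that TEAE rates in this trial will be diluted. No undosed count is given or implied, so the effect is conditional.
- A reader might take the 20% dropout assumption in Section 9.2 as the undosed fraction. It covers loss over the whole study, not failure to start.
- A reader might conclude that the synopsis consistently uses ITT for safety. Its Primary Safety Endpoints paragraph names the safety population.
- A reader might say that an undosed subject can never reach the numerator. The missing-onset rule leaves that possible.
- A reader might assume that the first dose is taken at home. The protocol says only bedtime; home dosing is a plausible inference.

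**Conclusion.** The inconsistency is real and the ITT wording in Section 9.11.1.1 is wrong as written for a TEAE table. Its size rests on an assumed number of undosed subjects. For 1 to 4 per arm, and setting aside the missing-onset exception, TEAE incidence would be understated by 1.4% to 5.6% of its value in the active arm and 2.8% to 11.1% in placebo. The same undosed count weighs twice as heavily in placebo because that arm is half the size. The understatement is zero if every randomized subject takes a dose, which the Visit 3 timing makes quite possible. This is a minor point that needs a wording correction. It bears on no planned test of adverse events, on no efficacy result and on no feature of the design.

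**What to change.** In Section 9.11.1.1 and in the synopsis under Statistical Analyses, replace ITT with the safety population, both as the analysis set and as the denominator for percentages. That matches Sections 9.3.1 and 9.11 and the synopsis under Primary Safety Endpoints. Restricting the TEAE tables to treated subjects also removes the missing-onset anomaly, because every subject in the table then has a first-dose date.

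The cost is two wording edits, best made before unblinding. Data collection, sample size and the efficacy analyses do not change. The one downside for the sponsor is that reported TEAE rates may be slightly higher.

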9.11.1.2 Laboratory Evaluations

Clinical laboratory data will be listed and summarized using conventional units. All laboratory parameters will be listed and sorted by subject, collection date and laboratory test. Shift tables will capture change from baseline (see [Section 9.4](#) Definition of Baseline) to visit 28/ET for each laboratory parameter, if feasible. Separate summary tables will be provided for mean absolute and percent change in plasma iPTH and serum total 25-hydroxyvitamin D, serum calcium, serum

CaxP product and phosphorus, and urine calcium:creatinine ratio. Proportions will be compared using a z-test or t-test, as appropriate.

9.11.1.3 *Vital Signs*

Observed VS values will be summarized descriptively at baseline and changes from baseline will be descriptively summarized by treatment group, CKD stage, age group and gender. Summaries will include n (%), mean, SD, median, minimum, and maximum. VS values will be listed.

9.11.1.4 *Physical Examinations*

Physical examination dates, whether a PE (including weight and height) is performed or not, abnormalities, if any, will be added to the medical history or reported as AEs as appropriate, and summarized by SOC and preferred term using MedDRA version 24.0 or higher.

9.11.1.5 *ECG*

12-lead ECG measurements will be assessed at the study sites at visit 3, 22 and visit 28/ET and results will be collected on the eCRF.

Observed ECG values for heart rate and the corrected QT interval will be descriptively summarized at baseline and changes from baseline will be summarized descriptively by treatment group at visit 28/ET. Summaries will include n, mean (%), SD, median, minimum, and maximum.

Shift in ECG categories (normal ECG, abnormal ECG – not clinically significant, abnormal ECG – clinically significant, missing) from baseline to visit 28/ET will be summarized descriptively in the form of frequencies and percentages.

The paired t-test will be used to perform within-subject comparisons between baseline and post-baseline values for heart rate and the corrected QT interval, if feasible.

Additionally, the two sample t-test will be used to perform pair-wise comparisons of change from baseline heart rate and corrected QT intervals between the treatment groups.

In the event of gross violations from the normality assumptions, the signed rank test will be used to perform the within-subject comparisons and a Wilcoxon rank sum test will be used to perform the pair-wise comparisons.

All ECG values will be listed.

9.11.2 *Secondary Endpoint Analyses*

The number (n, %) of subjects with hypercalciuria (>200 mg Ca/g creatinine), hypercalcemia (two consecutive visits with serum calcium >10.3 mg/dL) or hyperphosphatemia (two consecutive visits with serum phosphorus >5.5 mg/dL deemed to be study drug related) or serum confirmed CaxP product >55 (for Cohort 1) or >60 (for Cohort 2) will be compared between the treatment groups (active versus placebo) using the Cochran-Mantel-Haenszel test statistic (alpha=0.05) for overall efficacy of the multicenter results; the Chi-square test or Fisher's Exact test will be used for reporting the results in the separate strata.

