Subjects in both cohorts will reduce the dose by one capsule per week, as necessary, and no more frequently than at biweekly intervals, in the event that any one of the following four criteria are met: plasma iPTH is confirmed to be <35 pg/mL (for subjects with stage 3 CKD) or <70 pg/mL (for subjects with stage 4 CKD), serum calcium (corrected) is confirmed to be >10.3 mg/dL, serum total 25-hydroxyvitamin D is confirmed to be >100 ng/mL, or serum phosphorus is confirmed to be >5.5 mg/dL (ages 12 to <18 years) or >6.0 mg/dL (ages 8 to <12 years), provided that the investigator has deemed the elevated serum phosphorus to be related to study drug administration and has taken appropriate and persistent actions to control serum phosphorus by initiating or adjusting any phosphate binder therapy.

Dose reductions will be accomplished by consistently omitting doses on a specific day of the week, as follows:

- First dose reduction: Dosing will be omitted on all Mondays (M).
- Second dose reduction: Dosing will be omitted on all M and Wednesdays (W)
- Third dose reduction: Dosing will be omitted on all M, W and Fridays (F)
- Fourth dose reduction: Dosing will be omitted on all M, W, F and Sundays (S)

Any subject who requires a further dose reduction will terminate dosing with study drugs and immediately commence the 6-week FU period.

Subjects on dose reduction will be allowed an unscheduled safety visit if deemed appropriate by the investigator to have FU blood sampling within 48 hours of any dose reduction.

A summary of the initial and reduced weekly dose levels, in mcg units, after each of the four possible dose reductions appears in the table below:

Daily (mcg)	Weekly (mcg)	Weekly Dose (mcg)			
		1 st Reduction	2 nd Reduction	3 rd Reduction	4 th Reduction
60	420	360	300	240	180
30	210	180	150	120	90
0	0	0	0	0	0

Subjects will suspend dosing if plasma iPTH is persistently <30 pg/mL (three consecutive visits) or serum calcium (corrected) is confirmed to be >11.0 mg/dL, and resume when iPTH is ≥ 35 pg/mL and serum calcium is <9.8 mg/dL at the next lower dose level.

Primary Efficacy Endpoint:

The primary estimand is the reduction of mean plasma iPTH by at least 30% from pre-treatment baseline. The primary efficacy endpoint is the proportion of subjects in the intent-to-treat (ITT) population (age 8 to <18 years) attaining a mean decrease in plasma iPTH of at least 30% from pre-treatment baseline compared to placebo during the EAP.

Primary Safety Endpoints:

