Another study conducted in adults with SHPT, stage 3 or stage 4 CKD and VDI provided multiple-dose data on serum 25-hydroxyvitamin D₃, total 25-hydroxyvitamin D and total 1,25-dihydroxyvitamin D for population PK analysis [Sprague 2014]. In this study, subjects received daily bedtime doses of 30, 60 or 90 µg of CTAP101 or placebo for six weeks and were monitored for six weeks after the last dose. Mean serum 25-hydroxyvitamin D₃ increased gradually in a dose-proportional manner. The t_{max} after the last dose was 38–43 hours with a tendency toward higher values with increasing dose. Mean C_{max} , after adjustment for baseline values, was 28, 60 and 86 ng/mL for the 30, 60 and 90 µg groups, respectively. Calcifediol exposures, calculated as mean background-adjusted AUC, were dose proportional and the mean $t_{1/2}$ was between 25 and 50 days. Steady-state serum 25-hydroxyvitamin D₃ levels were not reached after six weeks of dosing.

The effect of alcohol on the release of calcifediol from CTAP101 Capsules was evaluated in an in vitro dissolution study. Concentrations of ethanol up to 40% by volume had no effect on the release of calcifediol.

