An Interactive Response System (IRS) will provide study treatment group assignments (using a computer-generated randomization code provided by the IRS vendor) and dosing adjustments. An independent, unblinded Data Safety Monitoring Board (DSMB) will oversee the IRS and verify the appropriateness of all dosing adjustments, and monitor subject safety and the effectiveness of CTAP101 Capsules at regular intervals. Members of the DSMB will also conduct periodic reviews of study conduct to verify that all required data are captured to a sufficiently high degree (>95%) and within specified time frames (usually within 5 days), and to promptly recommend appropriate corrective actions to address any noted deficiencies, in an effort to minimize missing data. Specific responsibilities and activities of the DSMB will be defined in the charter ratified at the pre-study organizational meeting. These responsibilities will include the completion of an interim analysis of the data obtained in Cohort 1 to justify a starting dose for Cohort 2, and an interim analysis of the data obtained from Cohort 2 to justify a starting dose for a separate phase 2 study in subjects having ages of 1 month to <8 years.

Subjects receiving treatment prior to study enrollment with calcitriol or another 1 α -hydroxylated vitamin D analog, or calcimimetics prior to study enrollment will forgo further dosing with these agents for the duration of the study and complete an 8-week washout period prior to baseline assessments. Subjects receiving vitamin D supplementation at a rate above 1,700 IU/day or 50,000 IU (1,250 mcg) per month prior to study enrollment must reduce the dose to ≤1,700 IU/day for the duration of the study and undergo an 8-week washout period prior to baseline assessments if serum total 25-hydroxyvitamin D is ≥30 ng/mL. The washout period is unnecessary if serum total 25-hydroxyvitamin D is <30 ng/mL. Subjects will complete a 6-week follow-up (FU) period after completing the 26-week treatment period or after early termination (ET).

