5.5 Overdose and Toxicity

CTAP101 Capsules contain calcifediol, which is a vitamin D metabolite. An increased serum calcium has been shown to be one of the first indicators of toxicity associated with vitamin D overdose and is frequently used as a surrogate marker of toxicity in patients treated with vitamin D therapy. Progressive hypercalcemia may require emergency attention. Acute hypercalcemia may exacerbate tendencies for cardiac arrhythmia and seizure, and may potentiate the action of digitalis. Chronic or repeated hypercalcemia can lead to generalized vascular and soft tissue calcification.

No specific antidote to CTAP101 Capsules exists. If overdose is suspected, the subject should be monitored closely and kept under observation by a physician. The $t_{1/2}$ of calcifediol is approximately 30 days in adult patients with stage 3 or 4 CKD. Possible clinical and laboratory events include hypercalcemia and hypercalciuria.

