7.2 Treatment Period (Weeks 1-26)

7.2.1 Visits 4-10 (Days 8-71)

- May occur ± 3 days of scheduled day
- AE assessment
- Concomitant medications

- VS measurements
- Blood samples drawn for:
 - Chemistry (partial panel)
 - Plasma iPTH
 - Serum total 25-hydroxyvitamin D

7.2.2 *Visits 11-12 (Days 83-84)*

- Must occur on the scheduled days
- AE Assessment
- Concomitant medications
- VS measurements
- Blood samples drawn for all subjects at 0 (pre-dose), 6 and 12 hours and additionally, only for subjects assigned to intensive PK evaluation, at -2, 2, 4 and 8 hours after dosing on Day 83 for:
 - Chemistry (partial panel)
 - Serum 25-hydroxyvitamin D₃, [REDACTED]
- Blood samples drawn at 24 hours ±4 hours before dosing on Day 84 for:
 - Chemistry (partial panel)
 - Serum 25-hydroxyvitamin D₃, [REDACTED]

7.2.3 *Visit 13 (Day 85):*

- Must occur on the scheduled day
- Urine pregnancy (for females of childbearing potential)
- AE assessment
- Concomitant medications
- Urine pregnancy (only for females of childbearing potential)
- VS measurement
- Urine chemistry and urinalysis
- Blood samples drawn at 48 hours ±4 hours before dosing for:
 - Chemistry (full panel) and hematology
 - Plasma iPTH
 - Serum total 25-hydroxyvitamin D
 - Serum 25-hydroxyvitamin D₃, [REDACTED]
 - [REDACTED]
- Drug accountability
- Patient reported palatability and acceptability

- Dispense assigned bottles of study drug

7.2.4 *Visits 14-21 (Days 92-169)*

- May occur ± 3 days of scheduled day
- Visits 14 and 16 are required only for subjects who underwent upward dose titration at visit 13
- AE assessment
- Concomitant medications
- VS measurements
- Blood samples drawn for:
 - Chemistry (partial panel)
 - Plasma iPTH
 - Serum total 25-hydroxyvitamin D

7.2.5 *Visit 22 (Day 183):*

- Must occur on the scheduled day
- Urine pregnancy (only for females of childbearing potential)
- AE assessment
- Concomitant medications
- VS measurements
- Urine chemistry and urinalysis
- Blood samples drawn for:
 - Chemistry (full panel) and hematology
 - Plasma iPTH
 - Serum total 25-hydroxyvitamin D
 - Serum 25-hydroxyvitamin D₃, [REDACTED]
 - [REDACTED]
- Patient reported palatability and acceptability
- Drug accountability

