7.3 Follow-up Period or Second PK Assessment

7.3.1 *Visit 23 (Day 190)*

- Must occur on the scheduled day
- Required only for subjects participating in the second PK assessment
- AE Assessment

- Concomitant medications
- VS measurements
- Blood samples drawn for:
 - Chemistry (partial panel)
 - Serum 25-hydroxyvitamin D₃, [REDACTED]

7.3.2 *Visit 24 (Day 197)*

- May occur ± 3 day of scheduled day
- Required only for subjects participating in the second PK assessment
- Concomitant medications
- AE assessment
- VS measurements
- Blood samples drawn for:
 - Chemistry (full panel) and hematology
 - Plasma iPTH
 - Serum total 25-hydroxyvitamin D
 - Serum 25-hydroxyvitamin D₃, [REDACTED]

7.3.3 *Visits 25-27 (Days 204-218)*

- Must occur on the scheduled days
- Required only for subjects participating in the second PK assessment
- AE Assessment
- Concomitant medications
- VS measurements
- Blood samples drawn for:
 - Chemistry (partial panel)
 - Serum 25-hydroxyvitamin D₃, [REDACTED]

7.3.4 *Visit 28/ET (Day 225)*

- May occur ± 3 day of scheduled day
- Concomitant medications
- AE assessment
- PE (including weight, height and BMI)
- VS measurements
- 12-lead ECG

- Urine chemistry and urinalysis
- Urine pregnancy (only for females of childbearing potential)
- Blood samples drawn for:
 - Chemistry (full panel) and hematology
 - Plasma iPTH
 - Serum total 25-hydroxyvitamin D
 - Serum 25-hydroxyvitamin D₃, [REDACTED]
 - [REDACTED]

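### Laboratory shift tables end at Visit 28/ET, for completers six weeks after treatment, so reversible on-treatment shifts can be missed in them, chiefly for full-panel tests

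*Combined protocol and SAP*

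**What the plan says.** Section 9.11.1.2 (Laboratory Evaluations) sets the end of the shift tables: change from baseline "to visit 28/ET for each laboratory parameter, if feasible". It names no on-treatment visit and no worst value for this purpose. It also promises that laboratory data will be listed and summarized, and it adds separate mean-change tables for iPTH, total 25-hydroxyvitamin D, calcium, phosphorus, the calcium-phosphorus product and the urine calcium:creatinine ratio. No visits are named for those tables.

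The visit schedule separates the end of treatment from that endpoint. Section 7.2.5 gives "Visit 22 (Day 183") as the last treatment visit, and Section 7.3.4 gives "Visit 28/ET (Day 225") as the last follow-up visit. Sections 7.2.3 (Visit 13, Day 85) and 7.2.5 (Visit 22) both list "Chemistry (full panel) and hematology", together with urine chemistry and urinalysis.

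On early stopping, Section 3.1 says: "Subjects will complete a 6-week follow-up (FU) period after completing the 26-week treatment period or after early termination (ET"). The synopsis dosing plan says that a subject who needs a further reduction after the fourth will stop study drug and "immediately commence the 6-week FU period".

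Laboratory parameters are among the primary safety endpoints (Section 9.8.2), and the safety analysis is mainly descriptive (Section 9.11).

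**The concern.** A shift table shows how many subjects in each arm move from one category to another, for example from normal to high. It does this without relying on anyone's judgment of clinical significance. To describe what happens on drug, it needs an on-drug endpoint. Here the only endpoint lies in the follow-up period, at least for subjects who complete treatment. A creatinine or liver-test shift present at Visit 13 or Visit 22 and gone by Visit 28 would be tabulated as no shift.

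At stake is the completeness of one display of a primary safety endpoint, in children with stage 3 or 4 CKD, for whom on-treatment renal chemistry is of obvious interest. Because most of the safety analysis is descriptive, no formal test would recover what this table leaves out for the full-panel analytes.

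**Working it through.** **1. Time off treatment at the shift endpoint (completers).**
- Inputs: Visit 22 is Day 183, with no window (Section 7.2.5). Visit 28 is Day 225 ± 3 days (Section 7.3.4).
- 225 − 183 = 42 days, and 42 / 7 = 6.0 weeks. This reproduces the 6-week follow-up stated in Section 3.1.
- With the window: 222 − 183 = 39 days and 228 − 183 = 45 days.

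**2. Comparison with the plan's own on-treatment window.** Section 6.6.9 ends the treatment-emergent period 30 days after study drug stops. Even the earliest Visit 28, at 39 days, falls outside it. For completers, the shift endpoint is a value at which a newly arising event would not be counted as treatment-emergent.

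**3. Which analytes have another dedicated table.**
- Calcium, phosphorus, calcium-phosphorus product: change tables (Section 9.11.1.2) and active-versus-placebo threshold comparisons (Section 9.11.2).
- Urine calcium: change table for the calcium:creatinine ratio (Section 9.11.1.2) and hypercalciuria proportions (Section 9.11.2).
- Creatinine, blood urea nitrogen, liver tests, hematology: the shift table, plus the general commitment to list and summarize.

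**4. Early termination.** The endpoint is labelled Visit 28/ET. The documents do not fix whether an ET sample is taken when drug stops or at the end of the 6-week follow-up. Section 9.2 assumes 20% dropout: 0.20 × 72 = 14.4 active and 0.20 × 36 = 7.2 placebo. So up to about 14 active and 7 placebo subjects could supply ET values, and the table may mix near-on-drug with off-drug results.

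**5. Residual exposure at Day 225, as context only.** With first-order elimination, the share of the drug-related 25-hydroxyvitamin D₃ increment remaining after 42 days is 2^(−42/h), where h is the half-life in days.
- h = 30 (Section 5.5: "is approximately 30 days in adult patients with stage 3 or 4 CKD"): 2^(−1.40) = 0.38.
- h = 25 and h = 50 (Section 1.12: "was between 25 and 50 days"): 2^(−1.68) = 0.31 and 2^(−0.84) = 0.56.

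So 44% to 69% of the increment would be gone, and the rest would still be present. These are adult half-lives, assumed here for children. They describe drug exposure, not how long any laboratory abnormality lasts.

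**6. After the change.** With the endpoint at Visit 22, time off drug falls from 42 days to about 0 to 1 day.

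**The case against.** The strongest reply is that the shift table is one display among several.

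- Calcium and phosphorus are measured at nearly every treatment visit and are the best-covered analytes in the plan, through the change tables and the threshold comparisons. This stands. A reader might infer that the plan understates on-treatment calcium and phosphorus shifts in general. The documents do not support that, because only the shift table is affected. The other routes have limits: hypercalcemia needs two consecutive high visits, hyperphosphatemia also needs a judgment that it is drug-related, and mean changes do not count subjects who change category.
- A reader might also infer that any abnormality resolving within 42 days goes unseen. That is not so. Clinically significant laboratory values are recorded as adverse events (Section 6.4.1) and tabulated by arm if treatment-emergent (Section 9.11.1.1). This stands, but that route depends on the investigator's judgment (Section 6.6.7), which a shift table does not.
- Creatinine, liver tests and hematology will still be listed and summarized (Section 9.11.1.2), and Section 9.1 provides for summaries by visit. This also stands. What is missing is a dedicated on-treatment display by category, not every summary.
- The residual-exposure figures might be read as the size of a bias toward no difference between arms. They cannot carry that. The documents give no off-drug time course for any of these analytes, and a persistent change would still show at Visit 28.
- The tables are descriptive and planned only if feasible, and no efficacy conclusion depends on them. This limits the weight of the point but does not remove it.

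**Conclusion.** The point holds for the shift tables themselves. As planned, their only endpoint for completers is 42 days (39 to 45) after the end of treatment, so on-treatment category shifts that reverse can be missed there. The gap is most material for creatinine, blood urea nitrogen, liver tests and hematology. It does not extend to the laboratory safety analysis as a whole.

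How many shifts would be missed cannot be estimated from the documents. That any would be missed assumes some reversible on-drug effect, which is plausible but not shown. The six-week gap is certain only for completers, because the timing of the ET sample is not fixed. The reading rests on the legible text; the exploratory parts of Section 9 are redacted.

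**What to change.** In Section 9.11.1.2 and the SAP:

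1. Define shift tables from baseline to Visit 22, or to the last on-treatment value when Visit 22 is missing.
2. Add shift tables from baseline to the worst on-treatment value. For full-panel tests this will usually rest on Visits 13 and 22 only, since these are the scheduled on-treatment draws, and a footnote should say so.
3. Keep baseline to Visit 28 as a separate table labelled as off-drug follow-up.
4. State whether an ET value counts as on-treatment or follow-up, for example by its interval from the last dose, so that the two are not mixed in one table.

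The cost is a few additional tables. No new sample, visit or procedure is needed. The definitions are best fixed before unblinding.
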